
2. Study aims

- Our research question is which of our current practices of covering cesarean section incisions is 1) most clinically effective at eliminating surgical site infection and 2) is most cost effective. Patient safety is paramount and we would want to use the most effective form of surgical site infection prevention bandage/covering – however we do not know which of our practice is more effective. This question is unique to both high risk patients (BMI = or > 40), which uses one type of covering versus our normal risk patients (BMI < 40).
- Our hypothesis is that a sterile silver impregnated silicone foam dressing (Mepilex Border Post-Op Ag) will be effective in maintaining a low surgical site infection rate in both high risk patients (BMI = or > 40) as well as in normal risk patients (BMI < 40). We believe using the Mepilex bandage will be a more cost effective strategy.
- Post-operative surgical site infections are uncommon in our practice (about 1%) they are clinically and financially significant complications of surgery. Strategies to minimize this known complication are essential. Our study is largely exploratory in that there aren't any adequate head-to-head studies that can help us guide our practice in selecting a wound-cover following cesarean.
- The primary clinical aim of this project is to compare and differentiate infection rates between our current two practices. The first practice that many of our OB/GYNs have selected (as part of their clinical practice, not this study) is prophylactic negative pressure wound therapy dressing (wound vac) in high risk patients (BMI = or > 40) and a standard sterile dressing in women who are normal risk (BMI < 40). This change in addition to our surgical site bundle have shown dramatic decreases in surgical site infections and many of our doctors want to continue

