on our success. Several other OB/GYNs have decided to switch to use a different approach (as part of their clinical practice, not this study) and use a silver impregnated silicone dressing (Mepilex Border Post-Op Ag) regardless of BMI. The study will focus on women who have had a cesarean section at Regions Hospital. There have been conflicting data on whether the wound vac strategy is more effective or similarly effective to not using a wound vac; there have been a paucity of research studies that look at this data. There is only a single study that is prospective and it is inadequately powered; the rest are retrospective studies that have conflicting results. There have been no head-to-head comparisons in the class of Mepilex and Mepilex-related products versus prophylactic wound vacs. Our doctors are already using the two sets of products however it is not currently being studied.

- The primary analytic goal of the project will be to look at the cost of the current practice and compare it to the cost of the proposed new practice/comparison practice both with and without incorporating the approximate costs of complications in the bullet point noted above. This is one of the most important points that our study will address, as it will help provide data to inform the fiduciary responsibility of obstetricians in caring for their patients. We will obtain national averages and multiple it by the number of additional patient encounters related to complications; additionally we will obtain billing information of patients with infectious complications to analyze actual differences in cost. We will also collect ICD-10 and CPT codes for hospital, lab and clinic bills during the hospitalization and the subsequent 30-day postoperative period. As part of the data abstraction, these items will be reviewed by two members of the study team to evaluate whether the costs are related to wound care and complications versus routine care. Toes will be broken by a third study team member. We will also analyze the total cost of care in the two groups.
- The secondary clinical goal is to compare the location of the infections (cellulitis, which is easily treated and shallow, versus an abscess; the different locations result in dramatically different treatment intensities such as outpatient antibiotics for simple cellulitis versus invasive inpatient drainage procedures for a complex abscess).

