- Study design will be in a prospective cohort trial. The first cohort will be patients who are having a cesarean section with OB/GYNs that prefer using paper bandages in patients with BMI <40 and prophylactic wound vacuum therapy in patients with BMI > or = 40. The second cohort will be patients who are having a cesarean section with OB/GYNs that prefer using Mepilex Border Post-Op Ag regardless of BMI.
- This will be a pilot study as infection rates are low enough that a full study would take several years. However, if difference between methods are large enough then the study would be able to reveal this (see sample size section for details)
- There will be two cohorts:

- 1) Cohort 1 - Normal risk (BMI < 40) – standard dressing (sterile gauze dressing)
High risk (BMI > or = 40) – negative pressure wound therapy / "wound vac"
- 2) Cohort 2 - Normal risk (BMI < 40) – silver impregnated silicone dressing
High risk (BMI > or = 40) – silver impregnated silicone dressing

b. Population

i. Inclusion/Exclusion Criteria [See Human Subjects items to be moved here]

- Inclusion/exclusion criteria: pregnant women who have a cesarean section; as the bandage will be applied when women are no longer pregnant (after fetus is delivered) they will technically not be pregnant at the time of inclusion in the study
- Women will be excluded from the study if their bandage / BMI are not compatible with the cohort scheme noted above (for example if the patient's OB/GYN uses a bandage that is different than a wound vac, paper bandage or Mepilex dressing).
- Specific diagnosis & procedure codes – pregnancy, cesarean section not having other abdominal surgery (example: concomitant hernia repair) except for with concomitant bilateral tubal ligation, which is often done with cesarean sections
- Specific demographic inclusion/exclusion criteria – women of child bearing age having cesarean section at Régions Hospital
- We will compare patients to a database of patients who have asked to be excluded from research, we will exclude patients who requested this. This information is kept in central HealthPartners databases.

ii. Sample size

- Sample size of records to be obtained – enrollment will be 2 years, 1000 women
- Sample size for the main analysis – anticipated follow-up of 75%, which would net 750 women

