- A rationale for selecting the sample size is provided and is summarized as due to a 0.5-3% post-operative infection rate in order to adequately power a study to find a difference – the records to be obtained would include all patient who satisfy the inclusion criteria, approximately 500 per year. Based on this study population and anticipated surgical site infection rate of 0.5% in best case scenario and 3% (both better than the national mean) with a power of 80% and alpha 0.05 we would need a study size of 862. As this is the first study of its kind in the comparison groups it would be clinically salient to find significance or not find it as both results would be clinically helpful in guiding obstetricians.
- Follow-up in the postpartum period is notoriously low, approximately 50%. After cesarean most women tend to at least follow-up for an incision check in the clinics or go to the emergency room and thus it would be reasonable to expect 75% follow-up based on author prior clinical experience.
- Counts of patients expected to be study-eligible are approximately 500 / year based on our standard variation in annual cesarean rates.
- Our two cohorts should be of similar size. Approximately half of the OB's have chosen each closure method as their method of choice. All surgeons have similar obstetric volume and so the total group sizes will likely be similar in size. There are no anticipated changes to the current practice over the next two years.

c. Data collection process

i. Process steps for identification of patients or records

- We will use obstetric logs (paper log), MIDAS (electronic log) and hospital/clinic EMR to identify any women who have a cesarean section at Regions hospital in the date window of interest.
- The PI and co-investigators will review the patient records in the bullet points above for surgical site infection. Currently the Infection Prevention department already does this; the charts of the patients identified will be abstracted. All patients in the study will have their charts abstracted as

well by the PI for suggestion of surgical site infection or for any potential complications related to the surgical site coverings (standard gauze bandage, silver impregnated silicone dressing or negative pressure wound therapy device). Any question will be reviewed by an additional co-investigator obstetrician; if there is a discrepancy then the third co-investigator will make a final determination.

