- Who will be the initial contact with potential subjects: there will be no contact with the patients or physicians performing services.
- What steps will be taken to avoid coercion or undue influence in the recruitment of subjects: Bandages will be selected by the patients' OB/GYN surgeon as part of routine surgery. The patient will not experience anything different from routine care as a part of this study. When patients are admitted to the hospital we will however let them know that we are completing a study and that they may opt out of our data analysis by informing their nurse or surgeon that they wish to opt out of the data collection. Women who do not have a c-section (aka those who are excluded) will not receive this information as they are already not part of the study.
- We do not anticipate any conflicts with other studies being completed on our patient population We will request a waiver of informed consent as we are not contacting the patients, collecting additional information about patients or modifying care for these patients. We are comparing the outcomes that patients have based on their surgeon's practices.
- Who will obtain consent? We believe that a chart-review type study such as this should be exempt from obtaining consent.
- Why are we requesting a waiver?
 - Our hypothesis is that infection rates will be similar in both arms of the comparison groups and thus we believe that this study will pose minimal risk. The study itself does not impart a particular bandage on the patient but looks to see whether there are differences in outcomes over a 30-day post-operative period; thus we do not anticipate any harm. Data will be collected presented in aggregate and protected health information will not be analyzed, which also demonstrates minimal risk.
 - We believe that patients should be given the opportunity to exclude themselves from the study analysis and thus we will not include patient's that have asked HealthPartners to not be part of research.
 - Consent is obtained for non-research procedures (the surgical procedure), the surgical procedure does include having a sterile dressing. It is up to the OB/GYN surgeon to

decide on the bandage to place. This would be done by any of the nursing staff or clinical providers who see patients; this is our current practice and would not change.

How will patients be notified:

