Descriptive statistics generally as mean or total; chi-squared, Students t-test, Fisher exact tests as appropriate. Regression may be difficult with low infection rates.

- Anticipate roughly 300-600 participants per cohort (after accounting for patient follow-up)
- Variables per section "E" above
- Silver impregnated silicone dressing versus wound vac/paper dressing will be 1 study analysis. Then stratification by arm will be completed
- Infection rate will be reported as number (proportion). Clinical significance will be $P<0.05$. Dichotomous/categorical data will be reported as a proportion. Continuous variables may be dichotomized versus kept as a scale depending on the analysis (for example in our $BMI > or = 40$ versus $BMI <40$ would be one example of dichotomized data). Hemoglobin a1c (a measure of diabetic control) would likely be dichotomized into <7 (preferred in pregnancy) versus >7 .
- Missing data will be analyzed on a per-participant basis—for example if there is a recent BMI and not one done the day of surgery that may be used. Missing data that is used will be reviewed by a second investigator for appropriateness, if not certain then a third investigator will opine as to the appropriateness as a tie-breaker.
- We will obtain hospital / practice billing data averages (for patient care in general) to multiply by the additional visits (ER, home healthcare or clinic), admissions, procedures and surgeries to increase the clinical salience of our analysis.
- [name] wrote the analysis plan and will complete the analysis plan. SPSS v25 or similar will be used. A statistician from the HealthPartners Institute Research Methodology Group will be used for post hoc analysis for additional insight. [name] is confident he can complete descriptive as well as analytic statistics based on prior studies. He has generally performed his own statistical analysis when performing original research; post hoc statistician analysis has been consistent with his findings in these studies.

f. Power analysis or statement of precision

The following study parameters were used to find an appropriate sample size:

Study Parameters:

Incidence, group 1:	0.5%
Incidence, group 2:	3%
Alpha:	0.05
Beta:	0.2
Power:	0.8

The following sample sizes would be needed to have adequate power with a dichotomous endpoint, two independent sample study:

Sample Size:

Cohort 1	431 (silver impregnated silicone bandage)

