- Identify any reasonably foreseeable risks for subjects – the risk (even with an informed consent waiver) are minimal. All of the interventions clinically are not part of this study. This is not research on pregnant women, per se, as the patient is no longer pregnant at the time she is randomized and the incisional bandage is placed. Thus there will be no risk to the developing fetus. There is no effect on lactation and thus there is no risk to the newborn.
- We minimize risks to patients as a matter of surgical principal by using typical sterile technique. We also minimize risks by removing all the bandages by the time the patient leaves the hospital so that way each incision is evaluated prior to the patient leaving. The alternative would be to wait until a clinic visit 1 week later (except for the gauze bandage), however we felt we would standardize and protect our patients best by removing the bandages prior to leaving. In our practice we found that many patients were non-compliant with care of 1-week bandages (bandages that go home with the patient and are removed after 1 week) and thus we do not want to keep the proposed bandages on for 1 week.
- There is a risk that patient data may be lost or viewed by others, however it is quite low as data will be password protected and encrypted as noted above. Furthermore patient identifiers will not be part of the data analysis and will be kept in a separate log. See Data Confidentiality and Privacy section.
- The direct benefit of the research is we can implement the lowest risk infection prevention bundle possible for cesarean sections; if there is no observable clinical difference then we can take into account the cost differences. Recently we tried switching the type of negative pressure wound therapy device we used (from a 3-day version to a 7-day version that is less expensive and smaller); our infection rate changed and we do not know if it is due to confounding or due to the device change – in hind sight we wish that we studied in the same way as proposed here to control for confounding variables.

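### Section 4.e makes P<0.05 the criterion for clinical significance and specifies no effect estimate or interval for the infection difference, so an important but less than six-fold difference would usually be labelled not significant and its possible size left unreported

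*Combined protocol and SAP*

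**What the plan says.** Section 4.e names chi-squared, Student's t and Fisher's exact tests, and then sets the reporting rule: "Infection rate will be reported as number (proportion). Clinical significance will be $P<0.05". No section specifies an estimate of the between-cohort infection difference or an interval for it. Section 4.f mentions precision in its heading but contains only a power calculation for 0.5% versus 3%.

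The aim is comparative (section 2): "The primary clinical aim of this project is to compare and differentiate infection rates between our current two practices". The waiver rationale in section 4.c expects no difference: "Our hypothesis is that infection rates will be similar in both arms of the comparison groups".

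The plan intends to use a null result. Section 4.b.ii says "it would be clinically salient to find significance or not find it as both results would be clinically helpful in guiding obstetricians", section 4.f says the study could change practice whichever way it comes out, and section 6 says "if there is no observable clinical difference then we can take into account the cost differences". That last condition is not defined.

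The plan also carries warnings. Section 2 calls the study largely exploratory, section 4.a calls it a pilot, section 4.f concedes that power may be inadequate, and section 4.g says a p-value above 0.05 may be a false negative.

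**The concern.** Difference tests suit an aim of comparing rates. The trouble is the label and what is left out beside it. A p-value mixes the size of a difference with the amount of data. When only a handful of infections is expected, P<0.05 picks out extreme splits and little else. A smaller excess, in either direction, would usually be reported as lacking clinical significance, with no interval to show how large an excess the data still allow.

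This matters because the result is meant to be acted on. Section 3 puts negative pressure therapy at $300-500 per patient and the silver dressing at $20, and section 8 expects the practice to be ready to change within weeks of the analysis. Someone weighing infection against cost needs to know what difference in infection the data cannot exclude.

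**Working it through.** **Inputs.** Enrolment is 1000 with 75% follow-up, so 750 analysed (4.b.ii). The cohorts are expected to be of similar size (4.b.ii), taken here as 375 each. The site infection rate is 0.8-2% (section 3), or about 1% (section 2). Alpha is 0.05, taken as two-sided. Tests are Fisher or chi-squared (4.e). The doubling is my illustration; the plan names no smallest important difference.

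**The plan's own figure.** With p1=0.005, p2=0.03 and mean 0.0175, two-sided with pooled variance:

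n = [1.96·√(2·0.0175·0.9825) + 0.8416·√(0.005·0.995 + 0.03·0.97)]² / 0.025² = (0.3635 + 0.1554)² / 0.000625 ≈ 430.7, so 431 per cohort and 862 in total. This matches 4.f.

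**Expected infections.** 750 × 0.8% = 6 and 750 × 2% = 15.

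**Splits needed for p<0.05 at 375 per cohort.** At totals of 6, 10, 12 and 15 infections, Fisher needs at least 6 vs 0, 9 vs 1, 10 vs 2 and 12 vs 3. Uncorrected chi-squared needs the same splits at these totals.

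**Chance of p>=0.05 under a true doubling.** Exact enumeration over two independent binomials: sum Bin(i; n, p1)·Bin(j; n, p2) over all pairs (i, j) whose test gives p>=0.05, with n=375.

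| True rates | Fisher | Chi-squared, uncorrected |
|---|---|---|
| *Site rate taken as the lower cohort's* | | |
| 0.8% vs 1.6% | 91% | 85% |
| 1% vs 2% | 88% | 82% |
| 2% vs 4% | 70% | 64% |
| *Site rate taken as the pooled rate* | | |
| 0.53% vs 1.07% (pooled 0.8%) | 95.5% | 88.5% |
| 0.67% vs 1.33% (pooled 1%) | 93% | 87% |
| 1% vs 2% (pooled 1.5%) | 88% | 82% |
| 1.33% vs 2.67% (pooled 2%) | 82% | 76% |

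**Other cohort sizes, lower-cohort rates of 0.8/1/2%.** With 300 per cohort, Fisher misses 94/91/77% and chi-squared 87/84/70%. With 500 per cohort (all 1000 women followed), Fisher misses 87/82/60% and chi-squared 81/76/54%. The upper end of 4.e's range, 600, cannot hold in both cohorts, since 2 × 600 = 1200 exceeds the 1000 enrolled.

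**The plan's contrast at 375 per cohort.** For 0.5% vs 3%, the same enumeration gives p<0.05 in 69% (Fisher) to 78% (chi-squared) of studies.

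**What an interval would show: 11 vs 4 of 375.**
- Rates are 2.93% and 1.07%, a difference of 1.87 points.
- Chi-squared: z = 0.018667 / √(0.02·0.98·2/375) = 1.83, p=0.07. Fisher p=0.11.
- Wilson limits are 1.65-5.18% and 0.42-2.71%.
- Newcombe lower limit: 1.87 − √[(2.93−1.65)² + (2.71−1.07)²] = −0.2.
- Newcombe upper limit: 1.87 + √[(5.18−2.93)² + (1.07−0.42)²] = +4.2.

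Similarly, 8 vs 2 gives Fisher p=0.11 and an interval of −0.1 to +3.7 points. Even a tie at 4 vs 4 leaves −1.8 to +1.8 points, against a site rate of about 1%.

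**The case against.** The strongest reply is that the plan already says most of this. Section 4.g gives the false-negative warning, and sections 2, 4.a and 4.f disclose an exploratory pilot with doubtful power. Clinical may simply be a slip for statistical. That stands: low power is not hidden, and it is not the defect here. What remains is that 4.e, the section that governs the analysis, states a rule that does not reflect the warnings and provides no estimate through which a reader could apply them.

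A reader might infer that the plan treats p>=0.05 as proof of similarity and then moves to the cheaper dressing. The documents do not support that. Section 6 does not mention a p-value, section 8 speaks of readiness rather than a decision rule, and section 2 plans the cost comparison "both with and without incorporating the approximate costs of complications", so an excess of infections would still enter the cost side. The narrower point survives: section 6's condition is undefined, and P<0.05 is the only criterion on offer.

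A reader might also infer that a non-significant result is likely whatever the truth. It is not: the plan's six-fold contrast would more often than not be detected. Nor should the Fisher figures be quoted alone. 4.e also allows chi-squared, which lowers the miss rates by about 6 to 7 points without changing the conclusion.

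Finally, counts by cohort will be reported, so anyone could compute an interval, and section 9 commits the manuscript to STROBE. The first is true, but the plan's main result should not depend on readers doing so. The documents do not say what STROBE would require here, so it cannot be counted as the remedy.

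**Conclusion.** The point holds as a fault in a stated rule. Followed literally, 4.e would label 11 vs 4 or 8 vs 2 infections as not clinically significant and report no interval. At 375 per cohort, a true doubling from 0.8-2% would be labelled that way in 70-91% of studies with Fisher and 64-85% with chi-squared.

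These figures assume equal cohorts, independent women, two-sided tests and the site's own rates. A doubling is illustrative. The claim does not extend to the 0.5% versus 3% contrast, does not allege undisclosed low power, and does not imply that a non-inferiority design is needed. It should be fixed because the study intends to act on null results and the remedy is cheap.

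**What to change.** In section 4.e:

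1. Replace clinical significance with statistical significance as the name for P<0.05.
2. Make the main result the infection risk difference (silver minus wound vac/gauze) with a two-sided 95% confidence interval by a small-count method such as Newcombe, overall and by BMI stratum. Define it by dressing, because 4.a and 4.f number the cohorts in opposite order. Note that it is unadjusted: dressing follows the surgeon's choice (the second cohort is patients of "OB/GYNs that prefer using Mepilex Border Post-Op Ag regardless of BMI"), and 4.e itself says "Regression may be difficult with low infection rates".
3. State, in line with section 4.g, that p>=0.05 alone is inconclusive and does not by itself satisfy the condition in section 6 for turning to cost.

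No non-inferiority margin is needed.

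**Cost.** A few lines of SAP text and an interval from the same 2×2 tables, with no extra data. The downside is that more results will be reported as inconclusive, especially within BMI strata, where the women and infections are divided further. The interval will not remove confounding by surgeon or patient.

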- Patient's will be informed via standard HealthPartners methods, which includes potential inclusion in research unless they request to be excluded.

Who will provide consent? We will ask for a waiver of informed consent.

How will you ensure that the subject understands the consent? We will apply for a consent waiver. In an opt-out manner if a patient requests to not be included we will respect the patient's privacy in making this decision as part of standard HealthPartners policies.

d. Outcome/endpoint and other variable definitions, and instruments used

Definitions: superficial surgical site infection- defined according to Centers for Disease Control and Prevention criteria as infection involving only the skin or subcutaneous tissue occurring within 30 days of surgery with at least one of the following: 1) purulent drainage from the wound or 2) organism identified by culture or wound deliberately opened by the surgeon. Cellulitis will be evaluated as 1) erythema noted in clinical progress notes with antibiotics administered or 2) diagnosis of cellulitis with antibiotics administered. Our secondary outcome was a composite wound complication, including superficial, deep, or organ-space surgical site infection; wound dehiscence; seroma; or hematoma that occurred within 30 days of surgery. Other secondary outcomes included 30-day readmission, 30-day reoperation, and need for antibiotic treatment for any indication. The chart will be evaluated for nursing or provider notes that indicate problems with the bandage. Chart abstraction will be completed to look for other salient complications or factors that were not predicted. Primary and secondary outcomes will be binary with comments possible. Number of clinical visits for complications, enrollment in home healthcare for wound care and length of hospital visits will be noted.

Chart review form will be electronic, it will have the following elements (there will be 3 charts to protect PHI and to blind the analyst from the intervention), all participants will have a study enrollment number to link the data for appropriate analysis:

First form:

MRN	From EMR
Study enrollment #	From 1-1000

Second form:

Study enrollment #	From 1-1000
Intervention	Binary: cohort 1 vs cohort 2
BMI	BMI rounded to the tenths spot

Third form:

Study enrollment #	From 1-1000
Age	#
Enrolled	Yes / no
Follow-up after discharge from home	Yes / no
Complication noted	Yes / no
Date complication noted	Date

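### Missing BMI may be replaced case by case with no time window or stated masking, although BMI sets the stratum in both cohorts and can exclude women from the gauze/wound-vac cohort only

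*Combined protocol and SAP*

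**What the plan says.** Section 4.e sets the general rule, "Missing data will be analyzed on a per-participant basis", and illustrates it with BMI: "if there is a recent BMI and not one done the day of surgery that may be used". It adds a check: "Missing data that is used will be reviewed by a second investigator for appropriateness", with a third investigator deciding if there is doubt. It does not define how old a recent value may be, which record to prefer when there are several, or whether the reviewers are kept unaware of cohort and outcome.

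BMI has two other uses in the plan.

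- **Eligibility.** Section 4.b.i states: "Women will be excluded from the study if their bandage / BMI are not compatible with the cohort scheme noted above". Section 4.a defines the scheme. One group of surgeons "prefer using paper bandages in patients with BMI <40 and prophylactic wound vacuum therapy in patients with BMI > or = 40"; the other group "prefer using Mepilex Border Post-Op Ag regardless of BMI".
- **Stratum.** After the overall comparison, section 4.e says: "Then stratification by arm will be completed". Section 3 describes the two contrasts as wound vac against silver at BMI 40 or more, and gauze against silver below 40.

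On the second chart-review form in section 4.d, BMI ("BMI rounded to the tenths spot") stands beside the cohort code and has no measurement date. Outcomes are on a third form. The stated purpose of splitting the forms, apart from protecting health information, is to blind the analyst.

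**The concern.** A single substituted number can decide whether a woman is analysed and in which stratum, and it does so differently by cohort. Suppose two women have a delivery BMI just above 40, no day-of-surgery record and an older BMI of 38. If the first had a wound vac, the older value makes bandage and BMI incompatible, and she leaves the study. If the second had silver, she stays and moves to the normal-risk stratum. The reverse also occurs: a low substitute keeps a gauze woman who would have been excluded on her delivery BMI. No BMI value can remove a silver woman.

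If the person choosing the value knows the cohort, and perhaps the outcome, the choice is open to unconscious selection. Agreement between investigators does not prevent that when they share the same knowledge and have no written criterion. Infections are rare here, so a few choices could carry weight, most of all in the high-risk contrast.

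**Working it through.** **1. The plan's own figure.** For 0.5% versus 3%, two-sided alpha 0.05, power 80%, equal groups, pooled variance and no continuity correction, the two-proportion formula gives 431 per cohort, 862 in total. This matches section 4.f. The BMI rule does not affect it. At the anticipated 75% follow-up (750/2 = 375 per cohort) power is 74.3%.

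**2. Which decisions depend on BMI.**

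| Bandage | BMI needed to stay in | Effect of a substitute BMI on the wrong side of 40 |
|---|---|---|
| Gauze | below 40 | wrongly excluded, or wrongly kept |
| Wound vac | 40 or above | wrongly excluded, or wrongly kept |
| Silver | any | stays in; stratum changes |

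The asymmetry comes from sections 4.a and 4.b.i. The substitution rule in 4.e is what makes it open to discretion.

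**3. Is the cohort visible?** BMI and cohort share a form (4.d). The operating-room nurse documents the bandage (4.c.ii). The principal investigator abstracts every chart for infection and covering-related complications (4.c.i) and also analyses the data (4.c.ii). Visibility is therefore a strong inference, but no sentence says that the missing-data reviewers are unmasked.

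**4. How far a substitute could be off (assumptions).** The shift is weight change divided by height squared. At 1.63 m, 5/1.63² = 1.9, 10/1.63² = 3.8 and 15/1.63² = 5.6 BMI units. For 5-15 kg the range is 2.1-6.2 at 1.55 m and 1.7-5.2 at 1.70 m. The documents give neither weights nor heights, and a value that is truly recent would shift less.

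**5. How many infected women are exposed.** Section 3 gives 4-10 infections a year, about half of them in high-risk patients in 2018. Over two years that is (4 to 10) × 2 × ½ = 4 to 10 infections at BMI 40 or above, both cohorts together. If 5-20% of women lack a day-of-surgery BMI (assumption), 0.05 × 4 = 0.2 to 0.20 × 10 = 2 of those infected women fall under the rule. Fewer would lie close enough to 40 to be reclassified, and fewer again would be in the wound-vac group.

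**6. Worst case for the overall comparison.** Place the 3% rate in the gauze/wound-vac cohort and remove infected women only (Fisher exact test).

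| Per cohort | Infections | None removed | 2 removed | 3 removed | 4 removed | 5 removed |
|---|---|---|---|---|---|---|
| 431 | 2 vs 13 | 0.007 | 0.012 | 0.021 | 0.037 | 0.063 |
| 375 | 2 vs 11 | 0.021 | 0.037 | 0.063 | 0.106 | 0.175 |

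It takes five removals at 431 per cohort, or three at 375, to pass 0.05.

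**7. The high-risk stratum (size assumed, 50-150 per cohort).** With 4 infections in all, even 0 vs 4 is not significant (p about 0.12). With 10, 2 vs 8 is not (p 0.09-0.10) and 1 vs 9 is (p 0.016-0.019). A lopsided result can flip: at 50 per cohort, 0 vs 6 gives p = 0.027, and excluding two infected wound-vac women (0/50 vs 4/48) gives 0.054.

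**The case against.** The strongest reply is that the exclusion scenario partly defeats itself. Surgeons in the gauze/wound-vac cohort choose the bandage by BMI. If no day-of-surgery BMI exists, the surgeon presumably worked from an earlier value, which is likely to be the one a reviewer would retrieve, so bandage and substitute would usually agree. This is inference too, but it is plausible and lowers the expected number of wrongful exclusions. It does not help where several records exist, and it does not stop a silver woman changing stratum.

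The plan does have a safeguard in the second and third investigators, and outcomes sit on a separate form. Both count in its favour. Neither supplies a criterion, a window or masking of those who fill in the value.

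It can also be said that this is a self-described pilot and that missing follow-up, about 25% of women, is the larger missing-data problem. That is fair on priority. It does not justify leaving a discretionary rule in place on the variable that decides eligibility and stratum.

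A reader might infer that moving one or two infected women changes the stratum result. The documents do not support that as a general statement. On the assumptions above, one or two is near the ceiling of those exposed, and most plausible splits of 4-10 infections are non-significant before and after. The observed rates would move; the conclusion usually would not.

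**Conclusion.** The point holds as a weakness in a stated rule. Substitution is discretionary, without a window or stated masking, on a variable that sets the stratum in both cohorts and can exclude only gauze or wound-vac women. It can therefore act differently by cohort.

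Its size cannot be fixed from the documents, which give no rate of missing day-of-surgery BMI and no BMI distribution. It is probably small: about 0.2-2 infected high-risk women exposed if 5-20% are missing. The overall comparison stays below 0.05 after two worst-case removals (p = 0.012 at 431 per cohort, 0.037 at 375). Within the overall comparison, reclassifying silver women has no effect.

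Two stronger readings should be avoided. One is that the reviewers are known to be unmasked; this is likely but not stated. The other is that the substitute BMI is several units too low; that rests on assumed weight gain and on reading recent very loosely. The change is worth making because it is cheap and events are few, not because a large bias has been shown.

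**What to change.** 1. In section 4.e, replace the BMI example with one rule for both cohorts: the last measured BMI within a fixed number of days before surgery (14, for instance), recorded with its date and extracted by someone without access to cohort or outcome. Add a BMI date field to the form. The form already sets a window for hemoglobin A1c (one year before to three months after), so this suits its design.
2. Amend section 4.b.i so that a woman with no qualifying BMI stays in the overall cohort comparison and is left out only of the BMI-stratum contrasts, in both cohorts. Without this amendment her compatibility cannot be checked and her status is undefined.
3. Report, by cohort, how many BMI values were not from the day of surgery and how many women were excluded for a BMI/bandage mismatch.
4. Add a sensitivity analysis that keeps mismatched women in their surgeon's cohort. A time window alone does not remove the one-sided exclusion.

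The cost is edits to two sections, one form field and a small data pull. The pull is new work: the database queries in section 4.c cover billing for women with infections or complications and the research opt-out check, not BMI for about 1,000 women. A few women will be lost from the stratum contrasts. The sample size and patient care are unchanged.
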